4.0 Study Intervention(s)/Investigational Agent(s)

Description: Transcranial Direct Current Stimulation (tDCS) - The tDCS will be performed with the TaskFlow Transcranial Electrical Stimulation device (TaskFlow-TES), IRB approved under different studies (STUDY00009059, STUDY00003506, STUDY00010333). The TaskFlow Transcranial Electrical Stimulation device (TaskFlow-TES) is a custom brain stimulation device developed in-house at the University of Minnesota. The performance of the Taskflow-TES device underwent laboratory bench testing to determine whether a programmed range of current levels (0.0 to 2.0 milliamps in 0.1 increments) was delivered by the device. The laboratory bench testing was conducted by a Biomedical Engineer, [name], Manager of the MnDRIVE Brain Conditions Noninvasive Neuromodulation Laboratory. For the tested range of 0.0 to 2.0 milliamperes, the deviation in delivered current was no more than 1%.

The FDA has deemed this device as a nonsignificant risk (NSR), however an NSR study is still subject to abbreviated investigational device exemption (IDE) requirements laid out in section 812.2(b) of the IED regulations (see FDA minimal risk letter). TaskFlow-TES is battery powered, communicates with the control computer via Bluetooth and monitors impedance and delivered current. To assess subject perceptions of the intervention, we will ask what treatment they believe they received each session.

Stimulation will consist of three periods: RampUp (30 sec), Constant (20 min), RampDown (30 sec). During the Ramp periods, 2 mA current will be delivered to both AF3 and AF4 with an ascending (RampUp) and descending ramp (RampDown) over 30 sec via two saline soaked electrode sponges ($\sim 25\text{cm}^2$; current density = 0.08 mA/cm²). Active tDCS: A 2-mA current will be administered via two circular carbon rubber core electrodes in saline-soaked surface sponges (25 cm²), placed in a neoprene headband with marked locations based on the 10-20 EEG system. The anodal stimulating electrode will be at location AF3, over left dorsolateral prefrontal cortex (DLPFC) and cathodal electrode at location AF4, over right DLPFC. Sham tDCS: For sham stimulation, the electrodes will be placed at the same positions as for active stimulation (F3 and F4), but current will be ramped down immediately after the initial 30 s ramp up period. Thus, participants will feel the initial itching sensation associated with tDCS but will receive no active current for the rest of the stimulation period. This method of sham stimulation has been shown to be reliable (Gandiga, Hummel, and Cohen 2006). To assess subject perceptions of the intervention, we will ask what treatment they believe they received each session. Executive Function Focused Cognitive Training Protocol. WM focused training occurs on a computer and consists of a variety of exercises selected to i) place demands on the executive and storage functions of working memory ii) adapt to challenge the participant's

PROTOCOL TITLE: Combining Neuro-Imaging and Non-Invasive Brain Stimulation for Clinical Intervention in Opioid Use Disorder

VERSION DATE: 2022-02-11

current ability level, iii) provide ongoing feedback, and iv) present novel stimuli across verbal, visual and spatial modalities. Training tasks are developed in-house. Tasks for each subject are delivered from our AHC-IS server (cnc2.med.umn.edu). Responses of subjects and session audio and video are saved on our AHC-IS server for analysis of training performance and engagement. The aim of using multiple tasks that require WM functions is to engage thalamocortical connectivity in a number of different ways to promote generalization. In this scheme, experimenters will monitor each participant's training and customize the intervention to balance challenge and engagement. In addition, each week participants will perform 4-minute versions of a word and a spatial 3-back task that will remain the same across all weeks (but differ from the assessment versions) to allow us to track training improvements using a constant difficulty level.

Participant effort will be rated by experimenters at each session using the Work Behavior Inventory (Bryson, Bell, Lysaker, & Zito, 1997). Just before the end of each training session, subjects will complete a brief questionnaire that also asks about their perceived engagement in the training that day, as well as their mood, previous night's sleep, discomfort, and their perceived experimental condition. Finally, at the end of each session, the participant will select the final task from an array of fun games, which we have found promotes agency and improves attendance.

4.1 Drug/Device Handling: We will use transcranial direct current stimulation (tDCS) to stimulate dorsolateral prefrontal cortex (DLPFC). TDCS is a non-invasive brain stimulation technique that can modulate brain connectivity. TDCS involves applying a weak electrical current (2mA or less) to the scalp via anodal and cathodal electrode sponges, causing either increases or decreases in cortical excitability, respectively. Research has shown in both healthy subjects and patients (e.g. Alzheimer's disease, Parkinson's disease, stroke, and depression) that tDCS has the potential to modulate synaptic strengthening and neurotransmitter-dependent plasticity underlying changes in behavior and learning (Lang et al. 2005).

4.2 Biosafety: N/A

4.3 Stem Cells: N/A

5.0 Procedures Involved

5.1 Study Design:

This study is double-blind, within subject, within study staff, and sham-controlled. The scientific integrity of the trial and the credibility of the data from the trial depend substantially on the trial design. A description of the trial design includes: In a double-blind randomized design, up to 250 individuals with a

PROTOCOL TITLE: Combining Neuro-Imaging and Non-Invasive Brain Stimulation for Clinical Intervention in Opioid Use Disorder

VERSION DATE: 2022-02-11

current opioid use disorder (OUD) diagnosis, age 18-60 years, enrolled in a methadone or buprenorphine treatment program and clinically stable will be recruited. Patients will receive 10 days (1 20-minute administration per day) of either (i) transcranial direct current stimulation (tDCS) to PFC or (ii) sham-tDCS. All subjects will perform cognitive training during tDCS intervention (active or sham) to prime the engagement of the NAcc-PFC brain circuit. Rest fMRI will be collected pre-intervention, at the midpoint of intervention, and post-intervention. The purpose for adding the midpoint MRI is to increase the statistical power of showing the trend of the experimental treatment's effectiveness over time. Follow-up interviews will be conducted 1- and 2-months after intervention completion to query substance use.

To examine generalization and durability effects of training, patients will be asked to complete the following tasks at pre-intervention, post-intervention, 1-month follow-up and 2-month follow-up: D-KEFS Trail Making Test, D-KEFS Verbal Fluency, D-KEFS Color Word, Digit-Span (WAIS-WISC), Intra-Extra Dimensional Set-Shift Task. Saliva/Urine tests checking for substance use will be administered at each follow-up timepoint.

5.2 Study Procedures:

Randomization: Random permuted blocks (subgroups of 4) will be used to ensure equal group assignment (active or sham tDCS) at predefined equally spaced points in the sequence of patient assignment. Blinding: Participants will not be informed on their assigned protocol. During consent, they will be informed that there is a 50% chance of receiving active tDCS or sham tDCS every visit for five study visits.

Participants who consent to the study and meet study criteria as per the screening evaluation will be asked to participate in up to 17 study visits over a period of up to two months. This time period includes 10 tDCS sessions over a period of up to 5 weeks.

Participants will also be asked to be available for in-person 1- and 2-month follow-up visits after intervention completion to query substance use and complete cognitive tasks. All sessions will be coordinated with participants' visits to the clinic to minimize burden.

VISIT ONE/Screening Visit: After the participant has agreed to be in the study and signed the consent, the participant will be interviewed by a research staff member from the University of Minnesota and asked questions about the participant's health history and clinical symptoms. Females who could potentially be pregnant will be tested for pregnancy and, if positive, will not be allowed to participate. If testing is refused, participation will not be allowed. If eligible, the participant will complete the Timeline Follow Back (TLFB) and other paper questionnaires reporting opioid use and craving levels. Participants will complete baseline measures for: D-KEFS Trail Making Test, D-KEFS Verbal Fluency, D-KEFS

PROTOCOL TITLE: Combining Neuro-Imaging and Non-Invasive Brain Stimulation for Clinical Intervention in Opioid Use Disorder

VERSION DATE: 2022-02-11

Color Word, Digit-Span (WAIS-WISC). The participant will then be asked to complete a series of questionnaires that assess behavior, personality and substance use. Day 1 assessments will take about 2 hours total. After consent and after the participant acknowledges full understanding of the intervention, the participant will be randomly assigned (with 50% chance) to receive either active tDCS or sham tDCS while the participant performs the reversal learning task (see description of intervention under day 3).

VISIT 2-3/PRE-INTERVENTION: The participant will undergo a pre-intervention assessment, lasting about 2 hours. During the assessment, participants will complete a series of questionnaires that assess opioid use and craving levels, behavior, personality and substance use.

The participant will also undergo a pre-intervention MRI, lasting about 2 hours. The MRI involves taking pictures of the participant's brain, from which the properties of certain brain tissues can be measured. While sometimes MRI scans are done for clinical purposes, the scans the participant will receive are being done for research purposes. Since these scans are not designed for clinical or medical reading, the participant's scans will not receive a clinical or medical interpretation. For the scan, the participant will be asked to lie down quietly on a bed, and the bed will slide into the scanner. Once the participant is inside the scanner, it will start to take the pictures. During the scan, the participant will simply lie quietly in the scanner with eyes closed while the scanner takes images of the participant's brain. The MRI scan will be performed at the University of Minnesota's Center for Magnetic Resonance Research.

The assessment visit may be performed before, same-day, or after the MRI visit for ease of accommodating the schedule of the scanner or participant.

VISITS 4-8: Will involve cognitive training tasks concurrently with tDCS, with tDCS for the first 20 minutes (46 minutes total per day). We will first explain to the participant what the training tasks entail and detail tDCS procedures. TDCS side-effects questionnaire will be administered daily before and after intervention.

During tDCS intervention (active) the participant will be seated in a reclining chair while the participant perform the reversal learning task. Total participation time for visits 4-8 will be about 1 hour each day, or about 5 hours over a period of 2 weeks.

VISITS 9-10/MIDPOINT: At the midpoint assessments and MRI, the participant will be administered the same cognitive assessments, and substance use questionnaires as Visit Two. Craving will be re-assessed and follow-up MRI scan with same procedures as Visit Three will be collected. Total participation time for Visits 9-10 will be about 4 hours.

PROTOCOL TITLE: Combining Neuro-Imaging and Non-Invasive Brain Stimulation for Clinical Intervention in Opioid Use Disorder

VERSION DATE: 2022-02-11

The assessment visit may be performed before, same-day, or after the MRI visit for ease of accommodating the schedule of the scanner or participant.

VISITS 11-15: Will involve cognitive training tasks concurrently with tDCS, with tDCS for the first 20 minutes (46 minutes total per day). We will first remind the participant what the tasks entail and detail tDCS procedures. TDCS side-effects questionnaire will be administered daily before and after intervention.

During tDCS intervention (active or sham) the participant will be seated in a reclining chair while the participant perform the reversal learning task. Total participation time for days 3-7 will be about 1 hour each day, or about 5 hours over a period of 2 weeks.

VISITS 16-17/POST-INTERVENTION: At the post-intervention assessments and MRI, the participant will be administered the same clinical assessments, cognitive assessments, and substance use questionnaires as Visits 9-10. Craving will be re-assessed and follow-up MRI scan with same procedures as baseline will be collected. Total participation time for Visits 16-17 will be about 4 hours.

The assessment visit may be performed before, same-day, or after the MRI visit for ease of accommodating the schedule of the scanner or participant.

IN PERSON FOLLOW-UP: The participant will be asked to return 1- and 2-months after intervention to fill out the same clinical, cognitive and substance use questionnaires that were administered on Visits 2, 9, and 16. Follow-up visits will be about 1.5 hours each. Subjects will undergo saliva/urine tests evaluating recent drug/alcohol use.

At follow-up timepoints, we will contact subjects two weeks prior to the next follow-up to coordinate scheduling with sufficient time so that data is collected as close to the target as possible.

Retention: To maximize participant retention we will have all consented participants fill out a “contact” document in which they will provide at least two telephone numbers to be reached and one home address. We will ask participants to provide the phone number of a good friend or relative who will know their whereabouts to help us re-contacting the participant if needed. Before follow-up appointments, we will call participants over the phone to confirm their attendance and we will send reminder cards through regular mail. If participants give their consent, we will also send a text to their contact phone number.

5.3 Study Duration:

- The anticipated duration an individual participant’s participation in the study is 2.5-4 months since recruitment.

PROTOCOL TITLE: Combining Neuro-Imaging and Non-Invasive Brain Stimulation for Clinical Intervention in Opioid Use Disorder

VERSION DATE: 2022-02-11

- The duration anticipated to enroll all study participants: Anticipated end date Summer 2022.
- The duration anticipated to complete all study procedures and data analysis: Anticipated end date Fall 2023.

5.4 Individually Identifiable Health Information: We have submitted the University's Privacy Office online application for data privacy and security review. We will print and upload the application with this protocol.

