3.0 Study Endpoints/Events/Outcomes

3.1 Primary Endpoint/Event/Outcome: In a double-blind randomized design, up to 250 individuals with a current opioid use disorder (OUD) diagnosis, age 18-60 years, enrolled in a methadone or buprenorphine treatment program and

PROTOCOL TITLE: Combining Neuro-Imaging and Non-Invasive Brain Stimulation for Clinical Intervention in Opioid Use Disorder

VERSION DATE: 2022-02-11

clinically stable will be recruited. We will recruit individuals who have been treatment with methadone or buprenorphine for at least 2 months. Patients will receive 10 sessions (2 5-day blocks of 46-minute daily tDCS intervention) of either (i) transcranial direct current stimulation (tDCS) to PFC or (ii) sham-tDCS. All subjects will perform cognitive training during tDCS intervention (active or sham) to prime the engagement of the NAcc-PFC brain circuit. Rest fMRI will be collected pre-intervention, after 5 sessions, and post-intervention. Follow-up interviews will be conducted 1- and 2-months after intervention completion to assess cognition, assess behavior, and query substance use. Dependent variables will be (i) change in NAcc-PFC FC across intervention imaging sessions, (ii) change in cognitive performance across intervention sessions, and (iii) substance use status 2 months after study participation. The Specific Aims are to determine if the intervention: (A1) is feasible and safe in individuals with OUD, (A2) induces circuit-based target engagement (an NIH funding requirement), (A3) induces cognitive performance changes, and (A4) is related to substance use status 2 months after study.

To evaluate feasibility (A1), withdrawal and retention policies are described in Section 12.0. To evaluate safety (A1), we will use the Treatment Side Effects Questionnaire to record intervention side effects. Based on our alcohol tDCS study and studies from other research groups, we hypothesize that the intervention will be feasible and safe.

To evaluate circuit-based target engagement (A2) we will compare brain activation change (from pre-intervention to post-intervention) between active tDCS and sham groups. We hypothesize that the active tDCS group will have a larger increase in brain circuit engagement than the sham group.

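### Section 5.2 has participants told at consent of five tDCS visits with a 50% chance at each, but the protocol assigns once and delivers ten; section 4.0 also labels one electrode site two ways

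*Combined protocol and SAP*

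**What the plan says.** The consent disclosure is in section 5.2, under Blinding. Participants are to be told that "there is a 50% chance of receiving active tDCS or sham tDCS every visit for five study visits".

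The rest of the current text gives ten sessions:

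- Section 3.1: "Patients will receive 10 sessions (2 5-day blocks of 46-minute daily tDCS intervention".
- Section 5.1: "Patients will receive 10 days (1 20-minute administration per day) of either (i) transcranial direct current stimulation (tDCS) to PFC or (ii) sham-tDCS".
- Section 5.2, the paragraph straight after the disclosure: "This time period includes 10 tDCS sessions over a period of up to 5 weeks".
- Section 5.2 visit schedule: tDCS at visits 4-8 and again at visits 11-15.

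On allocation, section 5.2 uses permuted blocks of four over the sequence of patients "to ensure equal group assignment (active or sham tDCS". The sentence just before the disclosure reads "Participants will not be informed on their assigned protocol". Under Visit One, after consent, "the participant will be randomly assigned (with 50% chance) to receive either active tDCS or sham tDCS". Section 15.3 treats sham versus active as a between-group factor.

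Section 4.0 gives AF3 and AF4 in the ramp description, and AF3 (anode) and AF4 (cathode) in the active-arm description. The sham sentence requires the same placement as the active arm, but labels that placement F3 and F4 in a parenthesis.

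**The concern.** The Blinding sentence governs what staff tell participants about allocation. Two things in it do not match the design. The count of five is wrong on any reading. The words about every visit can suggest that the condition is drawn afresh each time, when a participant in fact faces a 1 in 2 chance of sham throughout.

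This deserves correction because the protocol makes consent depend on demonstrated understanding. Sections 8.2 and 9.2 require comprehension questions and a capacity assessment, and exclude anyone who does not seem to understand the study. Section 4.0 also has participants say which treatment they believe they received at each session. Someone expecting a new draw each time might answer differently from someone who knows the condition is fixed. That consequence is plausible but not demonstrated.

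The electrode label matters for reporting and replication. The stimulation site is part of the definition of the tested treatment, and it should be stated one way for both arms.

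**Working it through.** **Number of sessions.** The visit schedule in section 5.2 gives 5 tDCS visits (4-8) plus 5 (11-15) = 10, which reproduces the ten stated in sections 3.1, 5.1 and 5.2. The disclosure states 5, and 5/10 = 50%.

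**Cross-check on visits.** Section 5.2 allows up to 17 visits: 1 (screening) + 2 (pre-intervention) + 5 (tDCS) + 2 (midpoint) + 5 (tDCS) + 2 (post-intervention) = 17. With a single block of five the total would be 17 - 5 = 12.

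**Cross-check on payment (section 11.4).**

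| Item | Amount |
|---|---|
| Screening and baseline questionnaires | 10 + 25 = $35 |
| Pre-intervention assessment and MRI | 25 + 25 = $50 |
| tDCS, visits 4-8 | 5 x 15 = $75 |
| Midpoint assessment and MRI | 25 + 25 = $50 |
| tDCS, visits 11-15 | 5 x 15 = $75 |
| Post-intervention assessment and MRI | 25 + 25 = $50 |
| Two follow-up visits | 50 + 50 = $100 |
| Total | $435 |

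This equals the stated total of $435. With five tDCS visits and nothing else changed, it would be 435 - 75 = $360, which does not match.

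**Unit of assignment.** No single sentence says that one assignment is kept for ten sessions. It follows from three statements read together: randomisation of patients in blocks, placed once under Visit One; ten sessions of either active or sham; and a between-group factor in the analysis. Under that design the chance of sham at all ten sessions is 0.50, and so is the chance of ever receiving active tDCS.

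**What the literal wording would imply.** If a participant took the sentence as an independent 50% draw at each of five visits, the chance of at least one active session would be 1 - 0.5^5 = 0.969, against 0.50 under the actual design. This shows how the misreading would differ. It does not measure any harm shown.

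**Electrode site.** In section 4.0, two statements give AF3/AF4 and one parenthesis gives F3/F4. Sections 2.2 and 4.1 name only the dorsolateral prefrontal cortex, so they do not settle the label. The active-arm definition and the instruction to use the same positions for sham both point to AF3/AF4.

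**Likely origin.** The amendment log records five sessions added for a total of ten, so the five is probably left over from the shorter schedule. Nothing above depends on the log.

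**The case against.** The strongest case on the other side is that these are copy-editing slips. The right number appears in the very next paragraph of section 5.2, delivery is fixed by several consistent statements, and the consent process adds explanation and comprehension checks. This largely stands, and it is why the point is minor. It does not remove the need to correct the text, because this is the sentence that sets the disclosure. Reading five as one of the two blocks does not rescue it either, since the sentence mentions no block and no second set of visits.

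A reader might infer more than the documents support:

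- *Only five sessions are delivered.* Every statement about delivery gives ten. Only the number disclosed is halved.
- *Participants are re-randomised at each visit, or cross over.* No such procedure is described. Section 5.1 does call the study within-subject, but next to the mention of study staff this most plausibly describes who is blinded.
- *The first block is active for everyone.* The visits 4-8 text says "During tDCS intervention (active) the participant will be seated in a reclining chair", whereas the text for visits 11-15 covers active or sham. Sections 3.1 and 5.1 give all ten sessions as either one or the other, so this is a clerical omission.
- *Participants were misinformed.* That depends on the consent form, which is not available here.
- *The arms were stimulated at different sites, or the site is unknowable.* The sham sentence requires the same placement as active, section 4.0 describes a headband with marked locations, and the defining text says AF3/AF4.

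**Conclusion.** The disclosure sentence is wrong as written. It gives 5 of 10 sessions, and its wording on every visit blurs a single 1:1 assignment. The electrode label in the sham sentence contradicts the active-arm definition in the same section. Both are minor corrections to operative text.

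The conclusion on session count rests on the current text alone. The conclusion on allocation rests on reading the randomisation, treatment and analysis statements together, as set out above. The documents give no basis for sizing any effect of either inconsistency, and neither changes the allocation, the number of sessions delivered, the analysis or the comparison between arms.

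**What to change.** In section 5.2, under Blinding, replace the sentence with: *You will be assigned once, by chance (1 in 2), to active or sham tDCS, and will receive that same treatment at all ten tDCS sessions.* Check that the consent form says the same. In the visits 4-8 text, refer to active or sham, as the visits 11-15 text already does.

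In section 4.0, change the parenthesis in the sham sentence to AF3 and AF4 after confirming the headband markings. If the headband proves to be marked at F3 and F4, correct the ramp and active-arm text instead.

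The cost is a wording amendment with IRB review. If the consent form carries the faulty sentence, it needs the same correction, and participants already enrolled should be told the correct allocation and session count. No procedures, visits or participants are added.
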